- t Only for females of childbearing potential. Serum pregnancy test will be done at Visit 1 only, and will be performed centrally. Patients determined to be pregnant will be discontinued from treatment and will no longer be administered investigational product (see Section 7.1). Patients will undergo urine pregnancy testing at the clinic during scheduled visits through Week 52. Additional urine pregnancy testing can be performed at the investigator's discretion. If required per local regulations, testing can occur at other intervals during the study treatment period and/or follow up period. Patients determined to be pregnant will be discontinued from treatment and will no longer be administered investigational product (see Section 7.1).
- u For the fasting lipid profile patients are not to eat or drink anything except water for 12 hours prior to test.
- v Where collection is allowed by local regulations.
- w Only serum and plasma are collected at this visit.
- x Immunogenicity samples may also be analyzed for ixekizumab serum concentration to facilitate in the interpretation of immunogenicity data. An additional blood sample will be collected, when possible, for any patient who experiences a potential systemic allergic/hypersensitivity reaction during the study as judged by the investigator.
- y PK samples are to be collected before investigational product injection.
- z The Week 52 MRI may be collected up to 10 days **prior** to Week 52 (Visit 15).

- aa Patients receiving investigational product who discontinue at any time prior to the end of the study or who complete the study (Week 52) and do not choose to enroll in Study RHBV, will have safety Follow-Up Visits 801 and 802 at 4 and 12 weeks (respectively) after the date of their last visit. Visit 803 will occur if a patient's neutrophil counts have not returned to the criteria defined in Section [8.4.10.1](#).
- bb Weight is only captured on eCRF at V2, V8, V10, V15, and/or ETV. Body weight collected at other visits is used only for calculation of creatinine clearance.
- cc If not completed at Visit 2, the sample should be collected as soon as possible at the next scheduled visit.

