6.1.1. General Considerations for Analyses during the Blinded Treatment Dosing Period (Period 2)

Comparisons between each ixekizumab regimen (80 mg Q2W or 80 mg Q4W) and placebo, as well as comparisons between adalimumab and placebo, will be performed for all analyses in Period 2.

Period 2 starts at the first injection of study treatment at Week 0 (Visit 2) and ends prior to the first injection of study treatment at Week 16 (Visit 8) or the ETV (between Weeks 0 and 16).

Baseline will be defined as the last available value before the first injection for efficacy, health outcome, and safety analyses. In most cases, this will be the measure recorded at Week 0 (Visit 2). For efficacy measures, if the patient does not take any injection, the last available value on or prior to randomization date will be used. Change from baseline will be calculated as the visit value of interest minus the baseline value. For safety analyses using a baseline period, the baseline period is defined as the time from Visit 1 to the date/time of the first injection.

The randomization to treatment groups is stratified by country and baseline CRP status (nonelevated versus elevated) as described in Section 5.2. The countries will be categorized into geographic regions for analysis. Geographic regions are defined in Section 6.2. Unless otherwise specified, the statistical analysis models will adjust for geographic region and baseline CRP status.

Unless otherwise specified, treatment groups of ixekizumab 80 mg Q2W and Q4W will be analyzed without regard to starting dose.

The primary analysis method for treatment comparisons of categorical efficacy and health outcome variables at specific time points will be made using a logistic regression analysis with treatment, geographic region (Europe and non-Europe), and baseline CRP status in the model using PROC Logistic with a Wald test. The odds ratio and 95% CIs will be reported; treatment difference and 95% CI will also be reported. Secondary analysis will be conducted using a Fisher's exact test. In the case when logistic regression model does not produce statistical results due to sparse data, Fisher's exact test will be used.

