6.1.4. General Considerations for Analyses during the Post-Treatment Follow-Up Period (Period 4)

For the safety analyses during Period 4, baseline is defined as the last non-missing assessment on or prior to entering Period 4, that is, on or prior to Week 52 (Visit 15), or ETV.

Safety data collected will be summarized using descriptive statistics.

Efficacy data collected during Period 4 will be summarized as described in Section 6.10.5.

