6.12.5. Vital Signs and Other Physical Findings

Analyses will be conducted on vital signs and physical characteristics including systolic blood pressure (mmHg), diastolic blood pressure (mmHg), pulse (bpm), weight (kg), BMI (kg/m²).

Change from baseline to last observation for vital signs and physical characteristics will be summarized for patients who have both baseline and at least one postbaseline result, for Periods 2, and 3, respectively:

- The scheduled visits/measurements will be included. The unscheduled visits and the repeat measurements will be excluded.
- For the Safety Population for Period 2, the comparisons between and among treatment groups will be conducted using an ANCOVA with treatment groups and baseline value in the model.
- Data will be analyzed based on original scale.

For vital signs and physical characteristics, the observed values at each visit (starting at baseline) and change from baseline to each scheduled visit, respectively, will be displayed in box plots for patients who have both a baseline and at least one postbaseline result. These box plots will be used to evaluate trends over time and to assess a potential impact of outliers on central tendency summaries.

- The scheduled visits/measurements will be included. The unscheduled visits and the repeat measurements will be excluded.
- The following summary statistics will be included as a table below the box plot: number of patients with a baseline and at least one postbaseline result, mean, standard deviation, minimum, Q1, median, Q3, and maximum.
- Data will be summarized based on original scale.

To assess the effect of administration of study drug on vital signs (blood pressures and pulse rate) among patients, at weeks 0, 16 and 20, vital signs will be measured before the first injection and 1 hour after the injection. The box plots will be produced for pre-dose and post-dose vital signs at Week 0 (Visit 2), Week 16 (Visit 8) and Week 20 (Visit 9).

The number and percentage of patients with treatment-emergent or follow-up emergent high or low vital sign and weight at any time for Periods 2, 3, and 4, respectively, will be summarized. The comparisons between and among treatment groups will be conducted using Fisher's exact test for the Safety Population for Period 2.

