- [Table RHBV.6.9](#) defines the high and low baseline values as well as the limits that are specified as treatment-emergent and follow-up emergent. Note that weight does not have an abnormal baseline; therefore, the treatment-emergent and follow-up emergent values are determined by change from baseline.
- All postbaseline scheduled, unscheduled and repeated measurements will be included.
- To assess increases, change from the maximum value during the baseline period or baseline to the maximum value during each study period will be used.
- To assess decreases, change from the minimum value during the baseline period or baseline to the minimum value during each study period will be used.
- For treatment-emergent high and low:
 - A treatment-emergent **high** result is defined as a change from a value less than or equal to the high limit at baseline to a value greater than the high limit at any time that meets the specified change criteria during the treatment period.
 - A treatment-emergent **low** result is defined as a change from a value greater than or equal to the low limit at baseline to a value less than the low limit at any time that meets the specified change criteria during the treatment period.
- For follow-up emergent high and low:
 - A follow-up emergent **high** result is defined as a change from a value less than or equal to the high limit at baseline to a value greater than the high limit at any time that meets the specified change criteria during the follow-up period.
 - A follow-up emergent **low** result is defined as a change from a value greater than or equal to the low limit at baseline to a value less than the low limit at any time that meets the specified change criteria during the follow-up period.

Table RHBV.6.9. Categorical Criteria for Abnormal Treatment-Emergent Blood Pressures and Pulse Measurement, and Categorical Criteria for Weight Changes for Adults

Parameter	Low	High
Systolic BP (mm Hg) ^a (supine or sitting – forearm at heart level)	≤90 and decrease from baseline ≥20	≥140 and increase from baseline ≥20
Diastolic BP (mm Hg) ^a (supine or sitting – forearm at heart level)	≤50 and decrease from baseline ≥10	≥90 and increase from baseline ≥10
Pulse (bpm) ^a (supine or sitting)	<50 and decrease from baseline ≥15	>100 and increase from baseline ≥15
Weight (kg)	(Loss) decrease from baseline ≥7%	(Gain) increase from baseline ≥7%

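### The SAP plans a follow-up emergent weight-change summary for Period 4, but the protocol captures no weight in the eCRF after V15 or ETV, and capture in Periods 2 and 3 is sparse

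*Protocol*

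**What the plan says.** **Protocol, Appendix 2 (Schedule of Activities).** Weight is marked at V1 and V2; at V5 to V8 in Period 2; at V9 to V15 and ETV in Period 3; and at V801, V802 and V803 in both Period 4 schedules (discontinuation before Week 16, and at or after Week 16). Every one of these rows carries footnote bb, which reads "Weight is only captured on eCRF at V2, V8, V10, V15, and/or ETV". About the readings taken elsewhere in the schedule, the footnote then adds: "Body weight collected at other visits is used only for calculation of creatinine clearance".

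**SAP Section 6.12.5 (Vital Signs and Other Physical Findings).** The SAP plans patient counts, with percentages, for any "treatment-emergent or follow-up emergent high or low vital sign and weight at any time for Periods 2, 3, and 4". Weight is there on purpose. The section explains that weight has no abnormal baseline, so "the treatment-emergent and follow-up emergent values are determined by change from baseline", and Table RHBV.6.9 sets the threshold at a 7% loss or gain. On which readings count, it states: "All postbaseline scheduled, unscheduled and repeated measurements will be included". The same section plans box plots of weight and BMI by visit.

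**SAP Section 6.1.4.** For Period 4 safety analyses, "baseline is defined as the last non-missing assessment on or prior to entering Period 4", that is, the Week 52 visit (V15) or ETV.

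**The concern.** The SAP defines a Period 4 weight analysis with a baseline, a threshold and an inclusion rule, while the protocol's data-capture rule supplies no postbaseline value for it. A stated safety summary would therefore come out with no patients contributing data, although sites weighed these patients at V801 and V802, and at V803 where needed.

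The same footnote thins the data behind the Period 2 and Period 3 summaries. A reader of a table headed as weight change at any time would assume that it draws on the visits at which weight was measured. In Period 2 it rests on one scheduled reading per patient. A change of 7% or more at Week 4, 8 or 12 that has reversed by Week 16 is seen at the site but not in the analysis.

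**Working it through.** No figure in the plan needs reproducing here. The check is a count of scheduled against captured weights, followed by a reading of the SAP rules on what is left.

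**Inputs.** Scheduled weights come from the weight rows in Protocol Appendix 2. Captured weights come from footnote bb. Period boundaries and baselines come from SAP Sections 6.1.1, 6.1.2 and 6.1.4.

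**Overall.** The numbered visits are V1 to V15 plus V801 to V803: 15 + 3 = 18. Weight is scheduled at all except V3 and V4: 18 − 2 = 16. The eCRF captures 4 of these 16 (V2, V8, V10, V15). ETV is additional.

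**Postbaseline, by period (captured share = captured ÷ scheduled).**

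| Period | Scheduled | Captured in eCRF | Share |
|---|---|---|---|
| 2 | V5, V6, V7, V8 (4) | V8 (1), or ETV for an early discontinuer | 1/4 = 25% |
| 3 | V9 to V15 (7) | V10, V15 (2), or ETV for an early discontinuer | 2/7 = 29% |
| 4 | V801, V802, and V803 as needed (3) | none (0) | 0/3 = 0% |

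**Period 4.** The V15 or ETV weight is the baseline, so it cannot also serve as a postbaseline value. Captured weights after it: 0. The percentage change has no numerator reading for any patient.

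**Period 2.** Section 6.12.5 assesses increases from baseline maximum to period maximum, and decreases from baseline minimum to period minimum. The baseline period runs from V1 to the first injection, but the V1 weight is not captured, so the baseline maximum and minimum are both the V2 value. Postbaseline, the only captured scheduled reading for a completer is V8, so the period maximum and minimum are both the V8 value. The rule collapses to V8 against V2, or ETV against V2 for an early discontinuer.

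**Period 3.** The rule collapses to the larger or smaller of Week 24 and Week 52, with ETV for those who stop early. SAP Section 6.1.2 also places the safety baseline of former adalimumab patients at Week 20 (V9). Weight is not captured at V9, so their last available captured value is the Week 16 reading (V8).

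**If all scheduled weights were captured.** Scheduled postbaseline readings per patient would rise from 1 to 4 in Period 2, from 2 to 7 in Period 3, and from 0 to 2 required (plus V803 if it takes place) in Period 4.

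**The case against.** The sparse capture is deliberate, and the footnote gives the purpose of the other weights. Protocol Section 8.4.2 defines vital signs as blood pressure and pulse, weight is not among the adverse events of special interest, and Protocol Section 9.5.3 does not name it. Baseline, Week 16, Week 24, Week 52 and ETV is a reasonable set for a descriptive measure. The words on timing in Section 6.12.5 are shared with blood pressure and pulse, which are recorded at every visit, so they may simply describe how available readings are used. This explains how the mismatch arose. It does not remove it, because the same section sets a specific rule for follow-up emergent weight and says which measurements count.

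Four stronger readings are tempting, and the documents do not support them.

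- *The empty Period 4 table would be read as zero events.* SAP Section 6.1 requires categorical summaries to show how many patients provide data, and suppresses percentages for zero counts. An empty row need not look like a 0% rate.
- *Incidence is understated unequally across periods.* Capture is 25% in Period 2 and 29% in Period 3, Period 4 has no rate to understate, and no comparison between periods is planned.
- *The Period 2 comparison between arms is biased.* Footnote bb applies identically to every arm. The documents give no ground for differential capture by treatment.
- *No Period 4 weight exists anywhere in the trial data.* Footnote bb speaks of the eCRF. Creatinine clearance is on the laboratory panel in Appendix 3, and weights may sit with that record. The documents do not say either way.

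**Conclusion.** The conflict between protocol footnote bb and SAP Section 6.12.5 stands. The Period 4 follow-up emergent weight summary cannot be produced from eCRF data: 0 of 3 scheduled follow-up weights are captured. In Period 2 the summary rests on V8 alone, or ETV; in Period 3 on V10 and V15, or ETV. Changes measured only at other visits are missed, which lowers sensitivity to the same degree in every arm.

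The point is small. Blood pressure, pulse, adverse events, efficacy, power and alpha are untouched. The change from baseline to last observation in Periods 2 and 3 is also largely served, because V8, V15 and ETV are all captured.

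The conclusion assumes that footnote bb was applied as written and that the creatinine clearance weights are not already available for analysis by another route. How many patients had a 7% change that reversed between captured visits cannot be estimated from the documents.

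**What to change.** **Preferred.** Enter the weights already measured at all scheduled visits, including V801 to V803, in the eCRF, or transfer them from the creatinine clearance record if they are held there. Amend footnote bb so that these weights may be used for the Section 6.12.5 analyses. The cost is a little more data entry, or one data transfer. No patient procedure is added.

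**If that is not done.** Delete weight from the Period 4 categorical summary in Section 6.12.5. Label the Period 2 weight result as at Week 16 or ETV, and the Period 3 result as at Week 24, Week 52 or ETV. Naming ETV matters: a label of Week 16 alone would be wrong for early discontinuers. This costs SAP wording only and remains possible even if the eCRF can no longer be changed.

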## Appendix 3. Clinical Laboratory Tests

---

### Clinical Safety Laboratory Tests to be Performed by Sponsor-Designated Laboratory

Hematology a :	Serum Chemistry a :
Hemoglobin	Sodium
Hematocrit	Potassium
Erythrocyte count (RBC)	Bicarbonate
Mean cell volume (MCV)	Chloride
Mean cell hemoglobin concentration (MCHC)	Phosphorus
Leukocytes (WBC)	Total bilirubin
Platelets	Direct bilirubin
Absolute counts of:	Alkaline phosphatase
Neutrophils, segmented	Alanine aminotransferase (ALT/SGPT)
Neutrophils, juvenile (bands)	Aspartate aminotransferase (AST/SGOT)
Lymphocytes	Blood urea nitrogen (BUN)
Monocytes	Uric acid
Eosinophils	Creatinine
Basophils	Calcium
Urinalysis (dipstick)a:	Glucose
Color	Albumin
Specific gravity	Cholesterol (total)
pH	Total protein
Protein	Calculated creatinine clearance b
Glucose	Creatine phosphokinase (CPK)
Ketones	Triglycerides
Bilirubin	Gamma-glutamyl transferase (GGT)
Urobilinogen	
Blood	Lipid panelc
Nitrite	Low density lipoprotein (LDL)
Urine creatinine	High density lipoprotein (HDL)
Leukocyte esterase	Very low density lipoprotein (VLDL)
Other Tests:	
Human immunodeficiency virus antibody (HIV) f	Pregnancy test (serum) d
Hepatitis B surface antigen (HBsAg) f	Follicle-stimulating hormone (FSH) e
Anti-hepatitis B surface antibody (HBsAb) f	Thyroid-stimulating hormone (TSH) and free T4
Anti-hepatitis B core antibody (HBcAb) f	Ixekizumab serum concentration (pharmacokinetic)
Anti-hepatitis C antibody f,h	Partial thromboplastin time (PTT)
HBV DNA g	Prothrombin time/international normalized ratio
High sensitivity C-reactive protein (CRP)	Exploratory storage samples (urine, serum, plasma, RNA, and whole blood)
Purified protein derivative (PPD) i	Pharmacogenetic sample (DNA)
Urine pregnancy test d (assayed by clinical study site)	Immunogenicity testing (anti-ixekizumab Ab)
QuantiFERON®-TB Gold test i	
T-SPOT® i	
HLA-B27	

**Clinical Safety Laboratory Tests**

Abbreviations: Ab = antibody; DNA = deoxyribonucleic acid; HBV = hepatitis B virus; RNA = ribonucleic acid; RBC = red blood cells; SGOT = serum glutamic oxaloacetic transaminase; SGPT = serum glutamic pyruvic transaminase; T4 = thyroxine; WBC = white blood cells.

- a Unscheduled blood chemistry, hematology, and urinalysis panels may be performed at the discretion of the investigator.
- b Cockcroft-Gault calculation is used for the calculated creatinine clearance.
- c For the fasting lipid profile, patients are not to eat or drink anything except water for 12 hours prior to test. Fasting is not required for the screening visit (Visit 1).
- d Serum pregnancy test for all women <60 years of age who are still of childbearing potential at Visit 1 only and will be performed centrally; after Visit 1, urine pregnancy test performed locally for women of childbearing potential.
- e Women  $\geq 40$  and <60 years of age who have had a cessation of menses for  $\geq 12$  months will have an FSH test confirming nonchildbearing potential ( $\geq 40$  mIU/mL).
- f Test required at Visit 1 to determine eligibility of patient for the study.
- g HBV DNA testing will be done in those patients who are HBcAb+ at screening.
- h See exclusion criteria (Section 5.2) specific to Hepatitis C antibody. A confirmatory test for HCV will be performed if the patient is positive for HCV antibody.
- i In countries where the QuantiFERON®-TB Gold test or T-SPOT® is available, either test may be used instead of the PPD TB test. The QuantiFERON®-TB Gold test may be performed locally or centrally; the T-SPOT® must be performed locally.

---

## Appendix 4. Hepatic Monitoring Tests for Treatment-Emergent Abnormality

---

Selected tests may be obtained in the event of a treatment-emergent hepatic abnormality and may be required in follow-up with patients in consultation with the Lilly clinical research physician, or its designee.

### Hepatic Monitoring Tests

---

#### Hepatic Hematologya

Hemoglobin  
Hematocrit  
RBC  
WBC  
Neutrophils, segmented  
Lymphocytes  
Monocytes  
Eosinophils  
Basophils  
Platelets

#### Hepatic Chemistrya

Total bilirubin  
Direct bilirubin  
Alkaline phosphatase  
ALT  
AST  
GGT

#### CPK

#### Haptoglobina

#### Hepatic Coagulationa

Prothrombin time  
Prothrombin time, INR

#### Hepatic Serologiesa,b

Hepatitis A antibody, total  
Hepatitis A antibody, IgM  
Hepatitis B surface antigen  
Hepatitis B surface antibody  
Hepatitis B Core antibody  
Hepatitis C antibody  
Hepatitis E antibody, IgG  
Hepatitis E antibody, IgM

#### Anti-nuclear antibodya

#### Anti-smooth muscle antibody

#### Alkaline phosphatase isoenzymesa

#### Anti-Actina

Abbreviations: ALT = alanine aminotransferase; AST = aspartate aminotransferase; CPK = creatine phosphokinase; GGT = gamma-glutamyl transferase; Ig = immunoglobulin; INR = international normalized ratio; RBC = red blood cells; WBC = white blood cells.

a Assayed by Lilly-designated or local laboratory.

b Reflex/confirmation dependent on regulatory requirements and/or testing availability.

---

## Appendix 5. Spondyloarthritis Features

---

To be included in Study RHBV, patients must have sacroiliitis defined radiographically according to the mNY criteria based on central reading

AND

at least one of the spondyloarthritis features (from Box 4, ASAS criteria for classification of axSpA [to be applied in patients with chronic back pain  $\geq 3$  months and age at onset of back pain <45 years]) bulleted below:

- **Inflammatory back pain (IBP):** According to experts, 4 out of 5 of the following parameters present: (1) age at onset <40 years, (2) insidious onset, (3) improvement with exercise, (4) no improvement with rest, (5) pain at night (with improvement upon getting up).
- **Arthritis:** Past or present active synovitis diagnosed by a doctor.
- **Enthesitis (heel):** Past or present spontaneous pain or tenderness at examination at the site of the insertion of the Achilles tendon or plantar fascia at the calcaneus.
- **Uveitis:** Past or present uveitis anterior, confirmed by an ophthalmologist.
- **Dactylitis:** Past or present dactylitis diagnosed by a doctor.
- **Psoriasis:** Past or present psoriasis diagnosed by a doctor.
- **Crohn's/Colitis:** Past or present Crohn's disease or ulcerative colitis diagnosed by a doctor.
- **Good response to NSAIDs:** At 24 to 48 hours after a full dose of NSAID, the back pain was not present anymore or much better.  
Note: As patients enrolling into the study should have failed 2 NSAIDs or be intolerant to NSAIDs, a doctor should assess whether patients had "good" prior response to NSAIDs.
- **Family history for SpA:** Presence in first-degree or second-degree relatives of any of the following: (a) AS, (b) psoriasis, (c) uveitis, (d) reactive arthritis, (e) IBD.  
Note: A doctor should confirm with his/her patient there was a clear diagnosis (not self-diagnosis) for any of these in first- or second-degree relatives.
- **HLA-B27:** Positive testing according to standard laboratory techniques.
- **Elevated CRP:** CRP >5.00 mg/L in the presence of back pain, after exclusion of other causes for elevated CRP concentration.

References: Rudwaleit et al. 2009; Sieper et al. 2009.

---

**Appendix 6. Protocol Amendment I1F-MC-RHBV(b)  
Summary: A Multicenter, Randomized, Double-Blind,  
Active and Placebo-Controlled 16-Week Study Followed  
by Long-Term Evaluation of Efficacy and Safety of  
Ixekizumab (LY2439821) in bDMARD-Naive Patients with  
Radiographic Axial Spondyloarthritis**

---

